7.2.3 Follow-up visits

All subjects who completed the clinical observation period in this clinical trial should be followed up for 5 years post-treatment in order to assess the long-term treatment effect with respect to recurrences of the sBCC target lesions and subject's safety. Follow-up (FU) visits will be scheduled 12 ± 1 months, 24 ± 2 months, 36 ± 2 months and 60 ± 2 months after completion of the 1st PDT cycle (Visit 5). Subjects who are drop outs should be encouraged to a final visit for safety documentation.

The following procedures will be performed at FU visits:

- Visual inspection of the treatment fields for any recurrent sBCC target lesion, and determination of size and location in case of recurrence.
- Assessment of esthetic appearance of the treated lesion(s) (treatment field(s)).
- Assessment of subject's satisfaction regarding PDT treatment and esthetic outcome.
- Documentation of relevant (S)AEs (any local AE or conditions within the treatment field(s) that may be relevant for proper assessment of the recurrence of the treated lesions or SAE that impairs the conduct of the study) and related SAEs (SARs) as well as the applicable concomitant medication to treat the relevant AEs/S AEs. Furthermore, any AEs that are considered relevant by the investigator will be documented.
- Documentation of new NMSC and melanoma, including location of lesion(s).
- Documentation of new AK lesions within the treatment field(s) and the treated subarea(s).
- Treatment of recurrent lesions with conventional therapy at the discretion of the investigator.
- The subject will be asked to return for the next follow-up visit, if applicable.
- Investigator will send a subject status confirmation by FAX or email (only for the last regular follow-up visit (FU4).

The results from the FU period of the study will be analyzed and reported separately, and are not part of the clinical observation period of the study.

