9 WITHDRAWALS

9.1 WITHDRAWAL OF SUBJECTS

Subjects must be withdrawn from the study (i.e. from any further study procedure) for the following reasons:

- At their own request (withdrawal of informed consent).
- If, in the investigator's opinion, continuation in the study would be detrimental to the subject's well-being.

Subjects must be withdrawn from the IMP under the following circumstances:

- Pregnancy (applies only during the clinical observation period of the study).
- If new lesions that develop in close proximity to a treated lesion after the 1st PDT require immediate treatment in the opinion of the investigator (during clinical observation period of the study).
- In case of a SUSAR or USADE.

In all cases, the reason for and date of withdrawal must be documented. Subjects are not obliged to specify a reason for their withdrawal. If they refuse to do so, the withdrawal should be documented as "withdrawal of consent". The subject must be followed up to establish whether the reason was an AE, and, if so, this must be documented in accordance with the procedures in [Section 8](#).

As far as possible, all examinations scheduled for the final study day should be performed on all subjects who receive the IMP but who do not complete the study according to protocol.

The investigator must make every effort to contact subjects lost to FU. Attempts to contact such subjects must be documented in the subject's records (e.g. at least 3 times and dates of attempted telephone contact, receipt for sending a registered letter).

For subjects that may not be randomized due to screening failures or who decide to terminate the study prior to randomization, at least the following parameters must be documented in the eCRF: date of informed consent, demographics and date and reason for withdrawal.

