11.2 ANALYSIS POPULATIONS

Treatment/clinical observation part of study

- Enrolled set: All subjects enrolled in this study i.e. that provided informed consent to participate in the study.
- Randomized set: All subjects randomized to IMP irrespective of whether they received IMP or not. The randomized set is the analysis set for the summary of subject discontinuation.
- Safety analysis set (SAF): all subjects treated at least once with IMP (IMP application). The assignment of subjects to the treatment groups will be as actually treated. The SAF is the analysis set for all safety analyses.

- Full analysis set (FAS): all subjects randomized and treated at least once with IMP and PDT (IMP application and illumination). In accordance with the intent-to-treat principle, the assignment of subjects to the treatment groups will be as randomized. The FAS will be the analysis set applied to the evaluation of primary, key secondary and further secondary endpoints.
- Per-protocol set (PPS): All subjects of the FAS without any major protocol deviations. The assignment of subjects to the treatment groups will be as actually treated. The PPS will be used for sensitivity analysis of the primary and key secondary endpoints and may also be used for selected analyses of secondary endpoints.

Follow-up part of the study

- SAF-FUP: all subjects treated at least once with the IMP entering the FU period.
- FAS-FUP: all subjects from the FAS of the clinical observation period entering the FU period.
- PPS-FUP: all subjects from the PPS (without any major protocol deviations) of the clinical observation period entering the FU period.

Further details will be specified within a separate SAP for the follow-up part of the study.

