## 4 Statistical Evaluation

Missing values of the primary endpoint will be regarded as non-responders. Missing values of clinical lesion assessments only will be imputed using a last observation carried forward (LOCF) approach. If no preceding assessment is available, the lesion will be regarded as non-responding. Further details of handling of missing data are described in section 4.6.

Unless otherwise stated, continuous data will be summarized by means of descriptive statistics, i.e. mean value, standard deviation (SD), first quartile, median, third quartile, range (minimum and maximum), and number of non-missing values. Categorical variables will be summarized by absolute and relative frequencies (percentages on non-missing values) of subjects by category.

Only data belonging to the clinical observation phase will be used for the analysis described in this SAP. For this, data of follow-up visits will be excluded from SDTM data sets used for analysis of clinical observation phase. For visit-scheduled datasets (incl. medical history), all records prior to or at Visit 8 (12 weeks post-PDT-3) - end of clinical study phase - will be included. Subjects with premature termination after Visit 8 will be removed from dataset "Study Termination" (i.e. they will not be identified as drop-outs). Furthermore, adverse events (AEs) and concomitant medications (CMs) starting after date of last visit/assessment of clinical phase (maximum date of all visit/assessment dates within non-log forms prior to or at Visit 8) on subject level will be excluded. If the month and/or day of the start date of AE or CM is not available, a worst-case-approach will be included when that assumed date is prior or at the maximum date of all visits and assessments prior to or at Visit 8. If the complete start date is not known, a worst-case-approach will be applied, and a date of 2000-01-01 will be assumed, to ensure that it will be prior to the maximum date of all visits and assessments prior to or at Visit 8.

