#### Frequency and extent of TEAEs, including SAEs

TEAEs are defined as all AEs with time of onset on or after the time of treatment with randomized IMP within 4 weeks (28 days) after each PDT cycle. If time of onset of AEs is not within 4 weeks (28 days) after each PDT cycle, but is identified to be at least possibly related to IMP or medical device, AEs will be assumed as TEAEs. The reference dates will be calculated as date of last PDT within each PDT cycle + 28, i.e. date of PDT-2 and/or PDT-4, respectively. If PDT-2 and/or PDT-4 are not available, the dates of PDT-1 and/or PDT-3 will be used for calculation of reference dates. These reference dates will be used for assignment of TEAEs. If unclear due to incomplete start time/date of AE or PDT, AEs will be assumed as TEAEs, as far as end time/date of AE is not before first treatment in first PDT cycle. AEs and TEAEs will be summarized and tabulated according to primary system organ class and preferred term displaying the number of events as well as counts and percentages on a subject basis per treatment arm.

[figure not shown]
Additionally, TEAEs by sex, TEAEs by age group I, serious TEAEs and TEAEs by intensity (mild/moderate/severe/unknown) will be tabulated. Related TEAEs (defined as possibly, probably, or definitely related, or with missing relationship) will be presented by intensity overall (related to IMP or related to medical device), related to IMP only, related to IMP and medical device and related to medical device only. Additionally, TEAEs by relationship (unrelated / unlikely related / probably related / probably related / definitely related) will be presented related to IMP and related to medical device separately.

TEAEs leading to death and TEAEs resulting in discontinuation of study will be tabulated if more than 5 events are observed. Specification of any action taken documented on AE page as 'Withdrawal from study' will be used for detection of TEAEs resulting in discontinuation of study.

A listing of subjects with TEAEs will be provided for all TEAEs reported. Non-TEAEs, i.e. AEs with onset before treatment or later than 4 weeks after each PDT cycle, will be listed separately for all subjects enrolled. In listings, the start day of the AE relative to start of treatment will be calculated for complete start dates only. Duration of events is only calculated for complete start and end dates.

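### SAP section 4's per-subject AE cut-off can remove events that SAP 4.5 defines as treatment-emergent in subjects who stop early

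*SAP*

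**What the plan says.** SAP section 4 restricts the analysis data to the clinical observation phase. AEs and concomitant medications "starting after date of last visit/assessment of clinical phase (maximum date of all visit/assessment dates within non-log forms prior to or at Visit 8" are the target, and these records "on subject level will be excluded". The date is each subject's own. No exception is made for TEAEs, SAEs or fatal events. One provision works in the other direction and keeps the event: "If the complete start date is not known, a worst-case-approach will be applied, and a date of 2000-01-01 will be assumed".

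SAP 4.5 defines the events to be tabulated: "TEAEs are defined as all AEs with time of onset on or after the time of treatment with randomized IMP within 4 weeks". This window runs to 28 days from the last PDT given in each cycle. There is a second route with no upper time limit. An AE with onset outside the 28 days that "is identified to be at least possibly related to IMP or medical device, AEs will be assumed as TEAEs".

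The protocol bears on this in five places:

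- Section 8.2 collects AEs from consent until Visit 5, or until Visit 8 if the subject is retreated.
- Section 9.1 says of withdrawn subjects: "The subject must be followed up to establish whether the reason was an AE".
- Section 7.2.3 describes who is followed long term: "All subjects who completed the clinical observation period in this clinical trial should be followed up for 5 years post-treatment".
- Section 11.2 defines the follow-up safety set: "SAF-FUP: all subjects treated at least once with the IMP entering the FU period".
- Section 11.3.4 promises an AE listing covering everything reported in all enrolled subjects.

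SAP section 5, which lists departures from the protocol, does not mention the cut-off.

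**The concern.** The rule is there to keep follow-up events out of the clinical-phase report, and for completers it does that. For a subject who stops early, the cut-off falls at a PDT visit, a phone call or Visit 4. An event that begins after that contact and keeps the subject from the next one brings about its own exclusion.

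The data would normally exist. Protocol 9.1 asks sites to find out whether an AE caused the withdrawal, and sections 8.3.1 and 8.4.1 require SAEs on the eCRF and to the sponsor within 24 hours. The rule is also uneven: an AE with a wholly unknown start date is kept, while one with a known date inside the TEAE window can be dropped.

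At stake is the completeness of the TEAE tables and listings for early stoppers. If early stopping differs by arm, the loss would differ by arm too. A disposition table could show an AE withdrawal or a death with no matching event in the safety output. The follow-up report does not recover it, because that report covers only subjects who enter follow-up.

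**Working it through.** The plan states no figure here, so there is nothing to reproduce. The check compares two dates: the end of the TEAE window (SAP 4.5) and the AE cut-off (SAP section 4).

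**Inputs** (SAP Table 1, with PDT-1 as day 0)

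- PDT-2: day 7 to 14
- Phone call 1: PDT-2 + 5 to 9 days
- Visit 4: day 28 to 42, nominal day 35
- Visit 5: day 77 to 91
- Window end: last PDT of the cycle + 28, which is day 35 to 42 if PDT-2 was given. If PDT-2 was not given, SAP 4.5 uses PDT-1 + 28.

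**Formula**

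Window days lost = max(0, last PDT + 28 − last recorded visit/assessment date)

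| Last recorded date | Calculation | Days lost |
|---|---|---|
| PDT-1 (no PDT-2) | 28 − 0 | 28 |
| PDT-2 | (PDT-2 + 28) − PDT-2 | 28 |
| Phone call 1, if its date counts | 28 − 9 to 28 − 5 | 19 to 23 |
| Visit 4, full range | smallest max(0, 35 − 42) = 0; largest 42 − 28 = 14 | 0 to 14 |
| Visit 4, nominal day 35 | 35 − 35 to 42 − 35 | 0 to 7 |
| Visit 5, not retreated | the visit falls 77 − 42 = 35 to 91 − 35 = 56 days after the window closes | 0 |

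Cycle 2 has the same spacing, so the same figures apply after PDT-3, PDT-4, phone call 2 and Visit 7, and Visit 8 loses 0 days. Events starting on the cut-off date itself are kept, because the rule removes only those starting after it.

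**Late related events.** For a non-completer, any at-least-possibly-related AE starting after the window is a TEAE under SAP 4.5 but falls after the cut-off whenever no later contact is recorded. For a completer, such an event starts after the final visit and so belongs to the follow-up period.

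**Weight of one subject.** With the planned numbers, one missing subject with an event moves a subject-level incidence by 1/37 = 2.7 percentage points on vehicle and 1/149 = 0.7 on active. This is a scale, not an estimate of how often it would happen.

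**After the fix.** If the cut-off is never earlier than the last PDT + 28, the formula gives 0 days lost in every row.

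**The case against.** A reader might infer that every AE after the last attended visit disappears, so that deaths and withdrawal-causing events in drop-outs appear nowhere in the trial. The documents do not support that, for these reasons:

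- **Dates that may count.** The cut-off uses all visit and assessment dates in non-log forms. Phone calls are scheduled contacts and the protocol allows unscheduled safety visits. SAP section 4 also names a study termination dataset. If its date counts, most fatal or withdrawal-causing events would be kept. The eCRF form list would settle this and is not in the documents.
- **Final visits.** Protocol 9.1 asks for the final-day examinations, as far as possible, in treated subjects who do not complete, and section 7.2.3 encourages drop-outs to attend a final safety visit. Either moves the cut-off later. Both are best-effort, and a hospitalised or deceased subject may have neither.
- **Onset governs.** An AE that began on or before the cut-off is kept even if death or withdrawal follows. Protocol 8.1.3 says most adverse reactions occur during or shortly after illumination, so days of window lost are not events lost.
- **Other records.** SAP 4.1 tabulates reasons for discontinuation, and SAEs reach the sponsor within 24 hours.
- **Fatal and discontinuation tables.** SAP 4.5 produces these only if more than 5 events occur. With fewer, a lost event affects the listings and the overall TEAE counts, not a dedicated table.

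A reader might also size the problem at 10%, or 15 of 149 active subjects. Protocol 11.6 and SAP 1.1 introduce that figure as missing histology. It is a sample-size assumption and says nothing about stopping at a PDT visit, the call or Visit 4.

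These points narrow the concern but do not remove it. Nothing in either SAP section exempts TEAEs from the cut-off, and section 4 does not say which dates count.

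**Conclusion.** The concern holds in a limited form. SAP sections 4 and 4.5 conflict for subjects who stop before their final clinical-phase visit: an AE with a known onset can meet the TEAE definition and still be excluded before TEAEs are tabulated or listed. The possible loss per cycle is the number of days in the table, plus later related AEs.

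This assumes that the rule is applied as written and that no later form date moves the cut-off. Under the widest reading of which dates count, little would be lost. Under the narrowest, a subject last seen at a PDT visit loses all 28 days after it. The number of subjects and events affected cannot be computed, because the documents give no rate of early drop-out or of AEs after last contact.

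Safety is analysed descriptively and no efficacy result depends on this. It is a gap in safety reporting, to be closed before unblinding. It is not evidence that deaths or withdrawals would go unrecorded.

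**What to change.** In SAP section 4, for subjects who do not complete the clinical observation period only:

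1. Set the AE cut-off to the latest of the last visit/assessment date, the last PDT + 28 days, and the study termination or last contact date.
2. State which form dates count, naming phone calls, unscheduled visits and study termination.
3. State that no AE meeting the SAP 4.5 TEAE definition, and no fatal AE, is removed by the cut-off in these subjects.

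Leave the rule unchanged for completers and report their later related AEs in the follow-up analysis. The protection in step 3 must stay limited to non-completers. The related-AE route in SAP 4.5 has no time limit, so applying it to everyone would pull follow-up events into this report.

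Add the cut-off to SAP section 5, since protocol 11.3.4 promises a listing of all AEs reported.

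The cost is a few lines of SAP text and a small programming change. No new data collection is needed.

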## 4.1 Dispositions of Subjects and Analysis Sets

## Disposition of subjects and analysis sets

The disposition of subjects and analysis sets, subjects per center, per visit and inclusion and exclusion criteria will be presented. Premature discontinuation from the study and completion of the clinical observation period will be summarized. Reasons for discontinuation will be tabulated. No inferential assessments will be performed on disposition data.

Tables will be created using enrolled set, randomized set, SAF, FAS, and PPS.

## 4.2 Demographics and Other Covariates

#### Demographic data

Demographic data (Age at inclusion, Sex, Center, Race, Ethnicity, Weight [lb and kg], Height [inch and cm], Fitzpatrick skin type group (type I-III, IV-VI) will be tabulated by treatment. Additionally age subgroups will be tabulated by treatment.

Demographic tables will be created using SAF, FAS, and PPS.

The abuse of any alcohol or drug at Screening will be tabulated using SAF.

#### BCC lesion characteristics

Baseline assessments of BCC lesion characteristics will be analyzed as follows:

Basic statistics for number of target BCC lesions, Baseline size of Main Target Lesion, and total area of target lesions at Baseline (summary of size of all target BCC lesions) will be presented on a subject basis by treatment. Additionally, the subgroups according to the total lesion area at

Baseline and to the size of the Main Target Lesion at Baseline will be tabulated by treatment. BCC lesion size of all Target Lesions will be additionally presented on a lesion basis.

The number of target Lesions at Baseline (1 vs.  $\geq$ 2 lesion(s)), the location of the Main Target Lesion, and location of all target BCC lesions (including combination of multiple locations) will be tabulated on a subject basis by treatment. Additionally, the location of target BCC lesions and the subgroup according to the size of target lesions at Baseline will be tabulated on a lesion basis by treatment.

The number of all lesions (target and non-target separately and in total) per treatment arm at Baseline will be tabulated.

Tables of BCC lesion characteristics will be created using SAF, FAS, and PPS.

#### Medical history

The proportion of subjects with any relevant medical and surgical history, any history of skin disease except for skin cancer, any history of skin cancer/actinic keratosis except for basal cell carcinoma, and any history of basal cell carcinoma will be tabulated.

Further details regarding medical history will be listed.

The medical history will be presented for the SAF.

#### Concomitant medication

Medications will be coded by the world health organization drug dictionary (WHO-DD).

Concomitant medication will be tabulated by Anatomical therapeutic chemical classification (ATC) level 1, ATC level 4, and WHO-DD preferred term using the SAF.

#### Fertility status and pregnancy test

Child-bearing potential, method of contraception and results of all pregnancy tests will be listed in detail for the SAF.

No inferential assessments will be performed on demographic and background characteristics.

## 4.3 Study Drug Administration

PDT details (duration of incubation, duration of illumination, duration of illumination excluding interruptions, number of illumination interruptions) will be tabulated by treatment, visit and illumination field using basic statistics.

Duration of illumination is calculated as follows:

Duration of illumination = Duration of illumination excluding interruptions + Total duration of interruptions.

Duration of illumination excluding interruptions will be set to 10 if illumination was done according to protocol.

The number of interruptions and total duration of interruptions will be set to 0 if the illumination was not interrupted for calculations only.

PDT details will be presented for SAF, FAS, and PPS.

Further PDT details will be listed.

No inferential assessments will be performed on study drug administration data.

## 4.4 Efficacy Analysis

Confirmatory hypothesis tests will be performed for the primary and the key secondary efficacy endpoints using a one-sided alpha level of 0.001. A one-sided 99.9%-confidence intervals (CI) will be additionally presented for the primary and key secondary endpoints. Hierarchically ordered hypothesis testing for the primary and the key secondary hypotheses will be used to ensure control of the family-wise error rate (FWER) (multiple type I-error level) of 0.1% (one-sided). Two-sided local (in terms of the subgroups) 95% confidence intervals (CIs) of differences between BF-200 ALA and vehicle will additionally be calculated for the primary and the key secondary endpoints.

Further secondary endpoints will be analyzed descriptively and in an exploratory way. For further secondary endpoints, two-sided statistical testing procedures will be conducted using a significance level of 5% ( $\alpha$ =0.05). Two-sided 95% confidence intervals (CIs) for the Mantel-Haenszel common odds ratio will be applied. Two-sided local (in terms of the subgroups) 95% confidence intervals (CIs) of differences between BF-200 ALA and vehicle will additionally be calculated for further secondary endpoints.

